9.4 Quality Assurance (Appendix III)

The end product of the Delphi methodology will comprise a technical manual and operation logbook, and a competency assessment tool, which will be used for pre-trial entry and to evaluate and measure adherence to agreed standards during the trial. A video and photographic methodology will be validated for use during the main COLOR III.

10 (HISTO)PATHOLOGY

All resected specimens are handled by one designated specialised pathologist per participating centre. Additionally, central review of the pathology will be performed (Dr. [name], dept. of Pathology, VUmc Amsterdam) and will include tumour typing, grading and assessment of histological prognostic factors. Participating pathologists will be requested to submit when possible, tumour and normal tissue for studies related to the research questions of the trial. All studies will be performed on tissue that has already been obtained from patients for diagnostic purposes. No tissue will be collected with the sole purpose of research. Written informed consent will be obtained from patients prior to tissue collection.

The pathology protocol is included in appendix IV.

10.3 Translational research

From the Dutch patients at least one block containing tumour tissue and one block containing normal tissue will be requested for biomarker side studies and will be processed anonymously. Informed consent for these side studies will be obtained. Within selected high volume centres blood samples will be collected and DNA is extracted for subsequent analysis of free circulating tumour DNA; (Separate protocol)

General aim

The general aim of translational research in the COLOR III study is to improve the clinical outcome of rectal cancer patients. Separate funding for this translational research project will be raised. We aim to validate molecular biomarkers to improve the clinical management of rectal carcinoma, thereby specifically addressing the following unmet clinical needs:

1. Identify the subgroup of rectal cancer patients at high risk to develop either local recurrence or metastatic disease (disease prognosis)
2. Develop minimal invasive diagnostics (e.g. blood sampling) for reading out tumour biology, to monitor disease recurrence (disease monitoring).

11 POSTOPERATIVE TREATMENT

11.1 Postoperative care

Analgesic care and allowance of restoration of diet will be according to an enhanced recovery program. It is required to be standardised for all patients in both treatment groups throughout the trial.

11.2 Postoperative chemotherapy

Currently there is no indication for adjuvant chemotherapy in the treatment of rectal cancer in The Netherlands. Postoperative chemotherapy should be administered according to local standards.

11.3 Postoperative radiotherapy

Currently there is no indication for adjuvant radiotherapy in the treatment of rectal cancer in The Netherlands. Postoperative radiotherapy should be administered according to local standards.

12 FOLLOW-UP

12.1 Follow-up visits

According to the international guidelines (ASCO, NICE) patients participating in the COLOR III trial are asked to visit the outpatient clinic yearly for a period of 5 years. More frequent visits and additional examination are only on indication or to the preference of the attending surgeon. A chest radiograph and a liver ultrasound or CT-thorax/abdomen are performed to assess development of distant metastases according to international guidelines. Follow-up of patients with recurrent disease should continue until at least 3 years after detection of recurrence or until death.

A CT or MRI of the pelvis must be performed three years postoperatively to assess possible local recurrence and/or residual mesorectum. In case of suspicion of recurrence on CT-abdomen a pelvic MRI is mandatory. In the NICE guidelines a minimum of two CTs of chest, abdomen and pelvis in the first 3 years is needed in the regular surveillance. The ASCO states that CT imaging of these regions is even needed annually in high risk patients. Since mid and low rectal cancer is associated with high recurrence rate and therefore patients should be marked as high risk patients compared to patients with a high rectal cancer and imaging of the pelvis after three years is considered standard of care.

12.2 Follow-up forms

Every year, the follow-up forms should be filled in and should be sent to the coordinating centre. Minor complaints or complications have to be noted in these forms. More serious complaints or complications necessitating hospital intake (unrelated to cancer) should be recorded in the form for events not related to cancer. In case of recurrent disease, the recurrence form and the recurrence follow-up form should be completed.

12.3 Questionnaires

To measure quality of life and functional outcomes, several questionnaires will be used. These questionnaires will be sent by email and access to an anonymized webtool (Castor) will be granted, if the patient does not have an email account, the questionnaires will be sent to the patients' home addresses, accompanied by a return envelope provided with postage stamps and the address of the hospital.

The following questionnaires will be used:

EQ 5D-5L (Euroqol): This questionnaire is a simple, generic instrument for describing and valuing health related quality of life. It includes 5 items (mobility, personal care, daily activities, pain, and anxiety-depression) that are answered on a 3-point scale ranging from no problems (level 1) to extreme problems (level 3).

Global quality of life (EORTC-QLQ-C30-QL2): This sub questionnaire contains the 2 items of the global quality of life dimension of the EORTC-QLQ-C30 questionnaire.

Global quality of life (EORTC-QLQ-CR29): This questionnaire is developed to assess the quality of life in colorectal patients.

LARS-score: Five questions (with at least one question representing each of the four known LARS symptom categories, namely incontinence, frequency, urgency and emptying difficulties) showing the highest prevalence and impact on QOL were identified.

Functional outcome and HRQoL after therapy will be measured using these validated questionnaires at admission and at 3, 6, 12, 24 and 36 months post-operatively.

	1 month	3 months	6 months	9 months	12 months	18 months	24 months	36 months	48 months	60 months
Clinical evaluation		X	X	X	X	X	X	X	X	X
CEA		X	X	X	X	X	X	X	X	X
Colonoscopy					X				X	
CT-thorax/abdomen or CXR and ultrasound liver			X		X	X	X	X	X	X
MRI-pelvis or CT-pelvis								X		
Functional outcome and HrQoL	X	X	X		X		X	X		

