3.3 Secondary endpoints/outcomes

Pathological

- Involvement of CRM (defined as tumour cells within 1mm from the lateral surface of the mesorectum, centrally reviewed by pathologists)
- Quality of specimen (as proposed and published by Quirke et al.)¹⁴
- Distal resection margin (defined as distance in cm from distal border of the tumour to distal resection surface)
- Translational research will be performed on predictive/prognostic biomarkers and imaging methods.

Clinical

- Length of hospital stay postoperatively (calculated as time from surgery to discharge in days)
- Morbidity within 28 days after surgery and within 90 days (graded by Clavien-Dindo Classification)
- Percentage of sphincter saving procedures (defined as colostomy percentage at 1 year postoperatively)
- Mortality within 28 days after surgery and within 90 days
- Local recurrence at five years (defined as cancer recurrence within the pelvic and perineal area)
- Disease-free survival at three and five years (calculated as time from surgery to last follow-up or date of recurrence)
- Overall survival at three and five years (calculated as time from surgery to last follow-up or death)

Quality of life

- Postoperative health related quality of life (quality adjusted life years) and functional outcome (measured with EORTC QLQ-CR29 and C30, EQ5D and LARS score). A difference of more than 10% in the EORTC list is considered significant.

See 'Chapter 12 Follow-up' for follow-up moments.

Costs (national) (sidestudy)

- In-hospital direct and indirect costs (measured with EQ5D and cost incremental analysis)
- Out-of-hospital postoperative costs (measured with EQ5D and cost incremental analysis)

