4 TRIAL DESIGN

The study is an international, randomised, non-inferior, multicentre trial comparing traditional and transanal laparoscopic TME as the surgical treatment for rectal cancer. Patients will be accrued by all participating hospitals participating in the COLOR III study group (list of participating hospitals can be obtained through rectalcancersurgery.eu → 'COLOR III Trial'). All centres will follow a quality assurance program of the procedure itself and the data before data will be entered in the COLOR III trial. The COLOR III study group is an international group of surgeons with interest and expertise in minimally invasive colorectal surgery.

The first COLOR study started in 1997 and completed a large RCT in 2003 comparing laparoscopic to open surgery for colon cancer.^{36,37} Hereafter, many centres of this study group joined the COLOR II study group. The COLOR II study group recently completed a major RCT comparing laparoscopic to open TME in the treatment of rectal cancer.

The design involves allocation of all appropriate consecutive patients with mid or low rectum carcinoma to either of the two procedures at a randomisation ratio of 2:1 in favour of the TaTME procedure. Once eligibility has been established and patient details have been noted, the patient will be allocated to either transanal or laparoscopic TME. Assignment to one the two treatment groups will not be blinded. Randomisation will be performed by computer and will be balanced by T-stage, preoperative radiotherapy, height of the tumour, BMI and gender. Data will be analysed on 'intention to treat' basis in case patients are not subjected to the randomised treatment modality. Randomisation will be done through internet: rectalcancersurgery.eu (click 'COLOR III Trial → Professionals').

Included surgical procedures to obtain TME are 1. low anterior resection (LAR) with colorectal anastomosis 2. LAR with coloanal anastomosis

Excluded surgical procedures are extralevator abdominoperineal excision (ELAP) (i.e. patients with tumour in growth (more than 1/3) in the anal sphincter complex or levator ani.

Exclusion criteria are T4 tumours, T3 tumours with a suspected involved CRM after neoadjuvant therapy, patients with concomitant metastases or other malignancies, with malignancies in their medical history or with signs of acute mechanical obstruction by the tumour.

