15.2 Data collected at randomisation

At randomisation, the clinician will be asked to give the following information through the internet:

- Eligibility criteria fulfilled?
- Randomising physician/surgeon
- Hospital (+ fax number)
- Type of planned surgery
- Patient: gender
- Patient: date of birth
- Clinical TMN stage

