15.3 Data collected during preoperative period

- ASA classification
- Length and weight
- Previous abdominal operations
- Medical history
- Date of diagnosis
- Location of the tumour on MRI
- Tumour characteristics
- Proposed type of resection
- Previous radiotherapy of the pelvis
- Preoperative (chemo)radiotherapy

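### Section 12.3 gives two different questionnaire schedules, and nothing places the baseline questionnaire before the unblinded allocation

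*Protocol*

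**What the plan says.** Section 12.3 of the protocol states the timing twice. The sentence after the list of instruments covers "Functional outcome and HRQoL" and schedules them "at admission and at 3, 6, 12, 24 and 36 months post-operatively". The table that follows has ten columns, from 1 month to 60 months. Its questionnaire row is marked at 1, 3, 6, 12, 24 and 36 months, and no row has a column before surgery.

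Section 3.3 lists the endpoint as "Postoperative health related quality of life (quality adjusted life years) and functional outcome" and refers the reader to chapter 12 for the measurement times.

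On allocation, section 4 says: "Once eligibility has been established and patient details have been noted, the patient will be allocated to either transanal or laparoscopic TME". It adds: "Assignment to one the two treatment groups will not be blinded". Section 17.1 places informed consent before randomisation. No section relates hospital admission to randomisation.

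**The concern.** The timing of a patient-reported outcome has to be fixed in the protocol, because a questionnaire that was not sent cannot be recovered by any later analysis. Here the two statements of the schedule differ at the earliest time point. That is the one that supplies either the pre-treatment value or the early postoperative value.

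The second issue is the position of the baseline relative to allocation. These scales are self-reported. If a patient already knows which operation is planned, the answers may reflect expectation about it, and the baseline is then no longer a pure pre-randomisation covariate. Adjusting for such a value can carry the expectation into the estimated treatment difference.

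The endpoints matter to the trial's argument. Local recurrence is tested for non-inferiority, and the hypothesis in the trial summary expects gains in function and quality of life to follow from fewer conversions, less morbidity and more sphincter preservation.

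**Working it through.** The protocol states no sample size or power for the questionnaires, so there is no figure to reproduce. The check compares the two schedules and then looks for any other section that settles the matter.

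**1. The two schedules in section 12.3**

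| Time point | Text | Table |
|---|---|---|
| Admission | yes | no column |
| 1 month | no | yes |
| 3 months | yes | yes |
| 6 months | yes | yes |
| 12 months | yes | yes |
| 24 months | yes | yes |
| 36 months | yes | yes |

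Each source has six time points, and five are shared. In the table, the questionnaire row is the only one with a mark at 1 month. The column therefore serves the questionnaires alone and is hard to read as a stray mark carried over from another assessment.

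**2. Does another section secure the baseline?**
- Section 3.3 only refers back to chapter 12.
- Section 15.2 begins "At randomisation, the clinician will be asked to give the following information through the internet" and lists eligibility, surgeon, hospital, planned surgery, gender, date of birth and stage. It lists no questionnaire.
- The section headed "15.3 Data collected during preoperative period" lists ASA class, body measurements, history, tumour data and prior treatment. It lists no questionnaire.

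The pre-treatment measurement therefore rests on the mention of admission in section 12.3 alone.

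**3. Order of admission and randomisation**
- Section 4 has patients allocated once eligibility is established and details are recorded.
- Section 5.1 restricts entry to elective surgery, and section 6.3 starts bowel preparation the day before the operation.
- Together these make randomisation before admission likely. No section states it.

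**4. What the 1-month point changes for quality-adjusted life years**

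The protocol gives no method for these. As an illustration, assume the usual area under the utility curve with straight lines between measurements, and treat admission as month 0. Write U0, U1 and U3 for utility at months 0, 1 and 3.
- Text schedule, months 0 to 3: (U0 + U3)/2 × 3/12 = U0/8 + U3/8.
- Admission and 1 month both measured: (U0 + U1)/2 × 1/12 + (U1 + U3)/2 × 2/12 = U0/24 + U1/8 + U3/12.
- Difference: U1/8 − U0/12 − U3/24 = (1/8) × [U1 − (2/3 U0 + 1/3 U3)].

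So the estimate moves by one eighth of the gap between the measured 1-month value and the value read off a straight line from admission to 3 months. The comparison between arms moves only if that gap differs between arms. With the table schedule alone there is no U0, and the first month has to be assumed.

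**The case against.** The strongest reply is that the table stands in the follow-up chapter and every column is a follow-up month. It has no preoperative column for any assessment, so the absence of admission there does not cancel the sentence above it, which requires an admission measurement. This stands. A reader might infer that the baseline will never be collected, but the text does not support that. The reply does not explain the 1-month mark, however. That is a follow-up time point, and the text leaves it out.

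A reader might also take it as fact that the baseline comes after randomisation. The protocol does not say so. The order is a reasonable inference for elective surgery, and the supported statement is only that the baseline is not fixed relative to allocation.

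Third, section 3.3 words the endpoint as postoperative, and the protocol states no baseline-adjusted analysis. The model may lie in a statistical analysis plan that is not at hand. This also stands, and for that reason a loss of precision should not be put on the point: any such figure would have to assume that no patient has a baseline and that adjustment was intended. But an analysis plan can only use data that the protocol has had collected.

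Fourth, all later questionnaires are also answered without blinding, so moving the first one does not remove expectation effects from the outcomes. That is correct. It would remove them only from the baseline.

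Finally, the 72 hours in section 17.2 might be read as a ready window for baseline forms. They are time to decide on participation, so they precede consent and show no interval between consent and randomisation.

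**Conclusion.** The point holds in a limited form. Section 12.3 contradicts itself at one time point in each direction: admission is in the text only, and 1 month is in the table only. No other section resolves this. Sites or a web tool could follow different schedules, some missing the baseline and others missing 1 month.

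Separately, nothing requires the self-reported baseline to precede an open allocation. That it may be answered with knowledge of the assigned operation rests on the assumption that admission follows randomisation, which is likely but not stated.

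The reach is confined to secondary endpoints: functional outcome, quality of life and quality-adjusted life years. The primary endpoint and its sample size are unaffected. The size of any bias cannot be calculated from the protocol. The only quantity that follows from the schedule is the one-eighth weight shown above, and it rests on the assumed area-under-the-curve method. The point merits correction because a baseline missed now cannot be obtained later, but it does not threaten the trial's main conclusion.

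**What to change.** 1. Add a baseline column to the table in section 12.3 and mark the questionnaire row in it.
2. State in the text that the baseline questionnaires are completed after consent and before randomisation, in place of admission. List them in section 15.2 or 15.3 as well, so that the data lists agree.
3. Decide whether 1 month is assessed, and make text and table say the same. If quality-adjusted life years are to be compared, the early postoperative value is a reason to consider keeping it.

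The cost is an edit to the protocol and to the web-tool schedule. The baseline set moves to an earlier moment and adds no questionnaire. Keeping 1 month adds one set compared with the present text. The downside is some incomplete baseline forms where randomisation follows closely on consent, since the protocol does not describe an interval between the two.

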13 RECURRENT DISEASE

Recurrences should be reported through the internet to the coordinating centre within 2 weeks after detection.

13.1 Definitions of recurrent disease

Evidence of recurrent disease is accepted when one of the following criteria is present:

- Local macroscopic tumour assessed by colono- or proctoscopy, (PET-)CT-scan or MRI of the pelvis
- Liver metastases on ultrasound, (PET-)CT-scan or MRI
- Lung metastases on chest radiography, (PET-)CT-scan or MRI
- Bone metastases on radiography, (PET-)CT-scan, MRI or bone scintigraphy
- Death with rectal cancer

13.2 Definitions of local recurrence

- Cancer recurrence in the pelvic or perineal area
- Positive (PET-)CT-scan or MRI (high resolution with T2 weighted imaging)
- Positive histology or cytology of adenocarcinoma

13.3 Treatment of recurrent disease

Treatment of recurrent disease should be according to local protocol and should be the equal in both treatment groups. Protocols have to be known to the main coordinating centre. Any changes in protocols throughout the trial period should be reported to and approved by the Protocol Committee. Treatment should be noted in the recurrence follow-up form.

13.4 Follow-up of recurrent disease

Follow-up of patients with recurrent disease should continue at least until 3 years after diagnosis of recurrence or until death. Recurrences and potential treatment should be noted in the recurrence form and the recurrence follow-up form.

14 STATISTICS AND DATA ANALYSIS

14.1 Sample size calculation

The primary endpoint is the local recurrence after 3 years. In laparoscopic TME the percentage of local recurrence is estimated 5%. A local recurrence increase of 4% is believed to be inferior. Based on this difference, sample size calculation has been done with a one-sided level of significance of 2,5% and a power of 80%. A total of 1104 patients is needed, 735 patients in the TaTME arm and 369 patients in the laparoscopic TME arm.

In this sample size calculation, additional postrandomisation analyses (drop-out, cross-over total 5%), is taken into account.

Randomisation will be stratified for

- T3a and less / T3b and more
- Downstaged with chemoradiotherapy: yes / no / NA
- Preoperative radiotherapy: yes / no
- Height of the tumour: 0-2.0cm / 2.1-5.0cm / 5.1-10cm
- Gender: male / female
- BMI \leq 30.0 / BMI $>$ 30.0

The randomisation will be executed in such a way that concealment of allocation for the indicating surgeon is guaranteed.

14.2 Statistical analysis plan

Baseline numerical data will be described in means, standard deviations or medians and interquartile ranges, baseline categorical data will be displayed in percentages. All comparative analyses will be conducted on an 'intention to treat' basis. Consequently, patients who are randomised to TaTME and converted to a laparoscopic or open TME, will be analysed in the TaTME group. Patients who are randomised to a laparoscopic resection and converted to TaTME or open TME, will be analysed in the laparoscopic group. Ninety days postoperative mortality, pathological resection margin and complication rates will be compared using the Chi-square test or an exact test if necessary. Local recurrence rate, disease-free and overall survival will be compared using the Log-rank test. Exploratory analysis of the prognostic effects of various baseline factors on disease-free survival will be carried out through multivariate Cox-regression. Apart from intention to treat analyses, per protocol analyses will be applied.

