The aim is to show non inferiority of TaTME compared to standard laparoscopic TME for mid and low rectal cancer local recurrence after 3 years of follow-up as primary endpoint. Secondary endpoints include morbidity and mortality, residual mesorectum on postoperative MRI, pathology, disease-free and overall survival, percentage of sphincter saving procedures, functional outcome and quality of life.

Statistics and randomisation

This trial is designed as a non-inferiority trial. The expected percentage of patients with a local recurrence after laparoscopic TME surgery is 5% after 3 years. TaTME is believed to be inferior to laparoscopic TME when there is a difference in local recurrence rate of more than 4% after 3 years in favour of conventional TME. Therefore, sample size is calculated based on non-inferiority with a difference of 4% with a one-sided level of significance of 2,5%, a power of 80% and a 5% drop-out rate. A total of 1104 patients is needed, 735 patients in the TaTME arm and 369 patients in the laparoscopic TME arm. Randomisation will be in a 2:1 ratio in favour of the TaTME procedure. It will be stratified for T-stage, preoperative radiotherapy, height of the tumour, gender and BMI. All analyses will be performed on intention-to-treat basis.

Main selection criteria

Patients with a histologically proved single mid or low rectum carcinoma (0-10cm from anal verge) on MRI, eligible for curative TME surgery with a intention for anastomosis, are included. Main exclusion criteria are T4 tumours, T3 tumours with a suspected involved mesorectal fascia (MRF) after neoadjuvant therapy, patients with concomitant metastases or other malignancies, with malignancies in their medical history or with signs of acute mechanical obstruction by the tumour.

Follow-up

Follow-up is based on international guidelines including imaging of the pelvis after three years with extra functional outcome questionnaires. Patients will visit outpatient clinic at least yearly for a follow-up period of five years. At the outpatient clinic the physician will carry out anamnesis and perform physical examination to check for distant metastasis and/or local recurrence. In case of the development of recurrence disease, follow-up should be pursued up to 3 years after diagnosis of recurrence.

Hypothesis

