The hypothesis is that TaTME will be non-inferior in mesorectum specimen quality and involved CRM and therefore will result in comparable rate of local recurrence. After TaTME which allows direct endoscopic visualisation we expect less morbidity due to less conversion rates and better anastomotic techniques. Moreover, the TaTME procedure will potentially enable more sphincter saving procedures. These expected results will have positive effect on functional outcome and health related quality of life.

FUNDING AND SUPPORT IN KIND

FUNDER(S) (Names and contact details of ALL organisations providing funding and/or support in kind for this trial)	FINANCIAL AND NON FINANCIAL SUPPORT GIVEN

KEY TRIAL CONTACTS

Trial Governors	Prof [name] (Chair Department of Surgery, VU University Medical Centre, Amsterdam) Prof [name] (Chief of Department of Gastrointestinal Surgery, Hospital Clinic, Barcelona) Prof [name] (Head of Division of Surgery, Imperial College, London)
Trial Co-ordinator	[name], [name]
Trial Contacts	[name], [name] VU University Medical Centre Department of Surgery [name], The Netherlands Email: [contact] [contact] [contact]
Protocol and Writing Committee	[name], [name], [name], [name], [name] , [name], [name], [name], [name], [name], [name], [name]
Statistician	[name]
COLOR III study group	All included centres; Follows

LIST OF CONTENTS

[figure not shown]
GENERAL INFORMATION	Page
TITLE PAGE	1
RESEARCH REFERENCE NUMBERS	2
SIGNATURE PAGE	3
TRIAL SYNOPSIS	4
TRIAL SUMMARY	5
FUNDING	7
KEY TRIAL CONTACTS	8
LIST OF CONTENTS	9
LIST OF ABBREVIATIONS	10
TRIAL FLOW CHART	12
STUDY PROTOCOL	
1. BACKGROUND	13
2. RATIONALE	16
3. OBJECTIVES AND OUTCOME MEASURES/ENDPOINTS	17
4. TRIAL DESIGN	19
5. ELIGIBILITY CRITERIA	22
6. PERIOPERATIVE CARE AND EXAMINATION	23
7. INVESTIGATIONAL PRODUCT	24
8. NON-INVESTIGATIONAL PRODUCT	25
9. SURGICAL PROCEDURE	26
10. (HISTO)PATHOLOGY	28
11. POSTOPERATIVE TREATMENT	30
12. FOLLOW-UP	31
13. RECURRENT DISEASE	32
14. STATISTICS AND DATA ANALYSIS	33
15. ADMINISTRATIVE ASPECTS, MONITORING AND PUBLICATION	34
16. SAFETY REPORTING	37
17. ETHICAL AND REGULATORY CONSIDERATIONS	43
18. REFERENCES	45
19. APPENDICES	48

LIST OF ABBREVIATIONS

AE	Adverse Event
APR	Abdominoperineal Resecton
AR	Adverse Reaction
cCRM	Clinical Circumferential Resection Margin
CI	Chief Investigator
CRF	Case Report Form

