Marks	2016	NR	0	25	0	0
Foo	2016	247,5	10	20	0	0
Buchs	2016	368,6	7,5	27,5	12,5	5

Our group published the results of our pilot study in which 80 patients underwent TaTME. Non conversions were necessary (COLORII 16%), anastomotic leakage rate was 4% (COLORII 13%). In 2.5% of the patients incomplete resection was found with CRM rate of 2.5% (COLORII 10%). In 0% of the patients a colostomy was created. Our results and the other series show that the rates of incomplete resection and permanent colostomies have decreased after TaTME compared with the laparoscopic TME. Furthermore, our results showed that TaTME is safe regarding short-term morbidity and mortality.

Conclusion

The new TaTME technique has potential advantages due to better visualisation and dissection in the lower pelvis. Less conversions and more sphincter saving procedures are reported in the cohort series. TaTME will probably resulting in a comparable mesorectum specimen quality and rate of involved CRM and therefore comparable rate of local recurrence. These expected results will have positive effect on functional outcome and health related quality of life.

Before adaptation of TaTME as standard surgical therapy for mid and low rectal cancer, a well-designed study is essential to demonstrate its efficacy and safety in a multicentre randomised setting: COLOR III trial. Furthermore, a major challenge in surgical cancer clinical trials is lack of consistency in surgical quality. This study aims at addressing this limitation by applying a robust surgical quality assurance protocol prior to the start and throughout the clinical trial to ensure consistency and validity.

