9.3 Conversion

In TaTME conversion (to either laparoscopic or open TME) is defined as interruption of transanal TME due to technical difficulties or complications during transanal dissection, requiring completion of the majority of the TME using an abdominal approach. In laparoscopic TME conversion is defined when completion of the dissection of the mesorectum is performed through a traditional open abdominal or transanal approach. Conversion is determined by the surgeon in case of concerns about patient safety, technical difficulties, inability to complete the TME procedure adequately or associated conditions that require treatment.

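### Control patients completed transanally dilute the intention-to-treat comparison towards non-inferiority, and the planned per-protocol analysis has no stated part in the conclusion

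*Protocol*

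**What the plan says.** The trial is a non-inferiority comparison of 3-year local recurrence with a 4-point margin, one-sided 2.5% significance and 80% power (Trial Summary, Statistics and randomisation; section 14.1).

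- **Cross-over is permitted.** Section 9.3: "In laparoscopic TME conversion is defined when completion of the dissection of the mesorectum is performed through a traditional open abdominal or transanal approach". The surgeon decides, on grounds of patient safety, technical difficulty, inability to complete the TME adequately, or associated conditions. Section 9.2 makes complete laparoscopic dissection a requirement for calling the operation a laparoscopic TME. The synopsis plans an interim look at conversions at 50% of inclusion and states no action threshold.
- **How these patients are analysed.** Section 14.2: "Patients who are randomised to a laparoscopic resection and converted to TaTME or open TME, will be analysed in the laparoscopic group". TaTME patients converted to laparoscopic or open TME likewise stay in the TaTME group.
- **Analysis set.** Trial Summary: "All analyses will be performed on intention-to-treat basis". Section 14.2 says the same of all comparative analyses, but its last sentence adds per-protocol analyses. It does not say what they contribute to the conclusion.
- **Allowance.** The synopsis and Trial Summary give 5% for drop-out. Section 14.1 says "additional postrandomisation analyses (drop-out, cross-over total 5%), is taken into account".

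**The concern.** A control patient whose mesorectal dissection is finished transanally has had at least part of the experimental operation. By section 9.2 that patient did not receive a laparoscopic TME, but is counted in the laparoscopic arm. If TaTME truly carries more local recurrence, such patients raise the control arm's rate and shrink the observed excess. In a superiority trial this works against the claim. In a non-inferiority trial it works for it.

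The usual protection is a per-protocol analysis that must agree with intention-to-treat. This protocol plans one, but two passages describe the analyses as intention-to-treat throughout, and none says what follows if the two sets disagree. The allowance in section 14.1 gives no protection here: a larger sample replaces lost patients and does not remove dilution. At stake is the error rate of the main oncological safety conclusion.

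**Working it through.** **1. Reproduce the planned sample size.** Inputs from the Trial Summary and section 14.1: control recurrence 5%, margin 4 points, one-sided 2.5%, power 80%, allocation 2:1, allowance 5%. No TaTME rate is given. The Hypothesis section expects that specimen quality will be non-inferior and "therefore will result in comparable rate of local recurrence", so 5% is assumed for both arms.

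Control n = (0.05×0.95 + 0.05×0.95/2) × (1.960 + 0.842)² / 0.04² = 349.5, so 350; TaTME 700; total 1050.

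Allowance: 1050/0.95 = 1105.3, so 1106; or 1050 × 1.05 = 1102.5, so 1103. The stated 1104 (735 + 369) lies between them. The 5% therefore acts only as inflation for lost patients. With 5% lost, 698 + 351 remain:

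SE = √[0.05×0.95×(1/698 + 1/351)] = 0.01426; power = Φ(0.04/0.01426 − 1.960) = Φ(0.845) = 80.1%.

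All of the allowance is used by loss, and nothing in the calculation represents cross-over.

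**2. Dilution under intention-to-treat.** Assumptions: true recurrence is 9% after TaTME and 5% after laparoscopic TME, exactly at the margin; recurrence follows the operation completed; a share c of control patients is completed transanally. Then:

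- control arm rate: p_c = 0.05 + 0.04c
- observed excess: 0.09 − p_c
- SE = √[0.09×0.91/698 + p_c(1 − p_c)/351]
- chance of a false claim = Φ((0.04 − excess)/SE − 1.960)

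For c = 5%: p_c = 0.052, excess 0.038, SE 0.01606, Φ(0.002/0.01606 − 1.960) = Φ(−1.835) = 3.3%.

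For c = 10%: p_c = 0.054, excess 0.036, SE 0.01621, Φ(0.004/0.01621 − 1.960) = Φ(−1.713) = 4.3%.

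| Control-to-TaTME cross-over (assumed) | Excess, points | False non-inferiority |
|---|---|---|
| 0% | 4.0 | 2.5% |
| 2.5% | 3.9 | 2.9% |
| 5% (whole allowance) | 3.8 | 3.3% |
| 10% | 3.6 | 4.3% |
| 20% | 3.2 | 7.0% |

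Enumerating the binomial outcomes for the same test gives 2.1%, 2.8% and 3.7% at 0%, 5% and 10%: slightly lower, with the same pattern. Cross-over from TaTME to laparoscopic would add to the dilution.

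**3. Cost of requiring both analyses.** Assume the per-protocol set is 5% smaller (663 + 333) and true rates are equal. SE = √[0.05×0.95×(1/663 + 1/333)] = 0.01464; power = Φ(0.04/0.01464 − 1.960) = Φ(0.773) = 78.0% for that set alone. Success in both sets is a little less likely. The sets are nested, so the two test statistics correlate at about √0.95 = 0.975, and the bivariate normal probability that both succeed is 76.3%.

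**The case against.** **Keeping converted patients in their randomised arm is correct.** This stands. The sentence in section 14.2 is not an error. The gap lies in what supports the intention-to-treat result.

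**The plan is not intention-to-treat only, and a SAP may settle the rest.** A reader of the Trial Summary might infer that no per-protocol analysis exists; the last sentence of section 14.2 shows otherwise. A reader might also infer that intention-to-treat decides if the two sets disagree; the protocol is silent on precedence. The definition of the per-protocol set may well be in a SAP that is not shown, and its absence here is not the point. What remains is that the protocol itself fixes the analysis set, in terms that do not agree with one another.

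**Cross-over is not unlimited.** Section 9.3 sets clinical conditions, section 9.2 requires laparoscopic dissection, conversions are an interim topic, and reasons for conversion are recorded (section 15.4). There is no numerical action threshold, but a reader should not infer free choice. Nor does the protocol say that every surgeon performs both operations; section 4 sets a minimum of two such surgeons per centre.

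**The background conversion rates are not cross-over rates.** A reader might set the 16% and 34% in section 1 against the 5% allowance. The 34% is conversion to open surgery. The 16% comes from COLOR II, which section 4 describes as laparoscopic against open TME, so it had no TaTME arm. Neither figure belongs in the calculation.

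**The model is simple.** A converted patient has already had some laparoscopic dissection, and section 1 says conversion is frequent in male or obese patients and in bulky or distal tumours. Such a patient's risk need not move cleanly from 5% to 9%. This stands, and it makes the figures indicative.

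**Per-protocol is not neutral.** Excluding cross-overs removes selected difficult cases after randomisation, so that analysis has a bias of its own. This stands too: it can support intention-to-treat but not replace it.

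**Conclusion.** The point holds in a limited form. The protocol permits control patients to be completed by the experimental approach, rightly keeps them in the laparoscopic arm, and gives the planned per-protocol analysis no part in the non-inferiority conclusion. Its statements on the analysis set conflict, and so do its statements on what the 5% covers.

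The effect is modest at the protocol's own allowance: false non-inferiority rises from 2.5% to 3.3% if the whole 5% is control-to-TaTME cross-over. It becomes material if cross-over is well above that, at 4.3% for 10%. These figures rest on true rates of 9% and 5%, on recurrence following the completed operation, and on assumed cross-over shares, since the protocol gives none. The change is worth making because it is cheap and also removes the conflicts; the documents do not show that the error rate is badly inflated.

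**What to change.** 1. Replace the Trial Summary sentence on intention-to-treat, and align the matching sentence in section 14.2, so that both name the two analyses.
2. Add to section 14.2: *Non-inferiority on 3-year local recurrence is concluded only if it is met in both the intention-to-treat and the per-protocol population.*
3. State how a case completed by the other arm's approach is classed per protocol, using the conversion definitions in section 9.3. Conversion to open stays in the allocated arm.
4. Report control-to-TaTME and TaTME-to-laparoscopic cross-over by arm, separately from conversion to open.
5. Reconcile the synopsis, Trial Summary and section 14.1 on whether the 5% covers drop-out alone or drop-out plus cross-over.
6. Note that the per-protocol set excludes selected difficult cases, so it supports the intention-to-treat result and does not replace it.

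None of this alters when a surgeon may convert. Both analyses are already planned, and section 15.4 already collects the type of resection and the reasons for conversion. The cost is power: if the per-protocol set is 5% smaller and true rates are equal, 80.1% falls to 78.0% for that set alone, and to about 76% for success in both.
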